3.3.2 Exclusion Criteria

1. Target Disease Exceptions

- a) Active brain metastases or leptomeningeal metastases. Subjects with brain metastases are eligible if these have been treated and there is no magnetic resonance imaging (MRI) evidence of progression for at least 4 weeks after treatment is complete and within 28-days prior to first dose of study drug administration. There must also be no requirement for immunosuppressive doses of systemic corticosteroids (> 10 mg/day prednisone equivalents) for at least 2 weeks prior to study drug administration. Subjects with incidental findings of asymptomatic brain metastases at screening may start study treatment without prior radiation treatment after discussion between the sponsor and investigator.

2. Medical History and Concurrent Diseases

- a) Any serious or uncontrolled medical disorder that, in the opinion of the investigator, may increase the risk associated with study participation or study drug administration, impair the ability of the subject to receive protocol therapy, or interfere with the interpretation of study results.
- b) Other prior malignancy active within the previous 3 years except for local or organ confined early stage cancer that has been definitively treated with curative intent, does not require ongoing treatment, has no evidence of residual active disease, and has a negligible risk of recurrence and is therefore unlikely to interfere with the primary and secondary endpoints of the study, including response rate and safety.
- c) Subjects with active, known or suspected autoimmune disease. Subjects with vitiligo, type I diabetes mellitus, residual hypothyroidism due to autoimmune thyroiditis only requiring hormone replacement, or conditions not expected to recur in the absence of an external trigger are permitted to enroll.
- d) Subjects with a condition requiring systemic treatment with either corticosteroids (> 10 mg daily prednisone equivalent) or other immunosuppressive medications within 14 days of first dose. Inhaled or topical steroids, and adrenal replacement steroid doses are permitted in the absence of active autoimmune disease.
- e) Prior therapy with experimental anti-tumor vaccines; any T cell co-stimulation or checkpoint pathways, such as anti-PD-1, anti-PD-L1, anti-PD-L2, anti-CD137, or anti-CTLA-4 antibody, including ipilimumab; or other medicines specifically targeting T cell is also prohibited.

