- f) All toxicities attributed to prior anti-cancer therapy other than alopecia and fatigue must have resolved to grade 1 (NCI CTCAE version 4) or baseline before administration of study drug. Subjects with toxicities attributed to prior anti-cancer therapy which are not expected to resolve and result in long lasting sequelae, such as neuropathy after platinum-based therapy, are permitted to enroll.
- g) Treatment with any chemotherapy, radiation therapy, biologics for cancer, or investigational therapy within 28 days of first administration of study treatment (subjects with prior cytotoxic or investigational products < 4 weeks prior to treatment might be eligible after discussion between investigator and sponsor, if toxicities from the prior treatment have been resolved to CTC grade 1 level).

- h) Subjects which have been previously enrolled and randomized in Studies BMS CA209331 or BMS CA209451 are not eligible.
- i) Inability to take oral medication or significant nausea and vomiting, malabsorption, external biliary shunt, significant bowel resection that would preclude adequate absorption of oral medication for subjects in the additional pancreatic cancer cohort only.

3. Physical and Laboratory Test Findings

- a) Positive test for hepatitis B virus (HBV) using HBV surface antigen (HBV sAg) test or positive test for hepatitis C virus (HCV) using HCV ribonucleic acid (RNA) or HCV antibody test indicating acute or chronic infection.
- b) Known history of testing positive for human immunodeficiency virus (HIV) or known acquired immunodeficiency syndrome (AIDS). NOTE: Testing for HIV must be performed at sites where mandated locally.
- c) Subjects must not be dependent on continuous supplemental oxygen use.
- d) For subjects assigned to the additional pancreatic cancer cohort: baseline echocardiogram showing left ventricular ejection fraction (LVEF) below the institutional lower limit of normal (LLN) or < 50%, whichever is lower, and electrocardiogram with corrected QT \geq 450 ms should be excluded.

4. Allergies and Adverse Drug Reaction

- a) History of allergy to study drug components.
- b) History of severe hypersensitivity reaction to any monoclonal antibody.

5. Sex and Reproductive Status

- a) WOCBP who are pregnant or breastfeeding.
- b) Women with a positive pregnancy test at enrollment or prior to administration of study medication.

6. Other Exclusion Criteria

- a) Prisoners or subjects who are involuntarily incarcerated

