Echocardiogram (additional pancreatic cancer cohort only)	X	Subjects with LVEF below the institutional LLN or < 50%, whichever is lower, and corrected QT \geq 450 ms are to be excluded
ECG	X	Within 14 days prior to first dose
Assessment of Signs and Symptoms	X	Within 14 days prior to first dose
Laboratory Tests	X	CBC w/differential, Chemistry panel including: LDH, AST, ALT, ALP, T.Bili, BUN or serum urea level, creatinine, albumin, Ca, Mg, Na, K, Cl, glucose, amylase, lipase, TSH, Free T4, Free T3, hepatitis B surface antigen (HBV sAg), and hepatitis C antibody (HCV Ab) or Hepatitis C RNA (HCV RNA), CPK (additional pancreatic cancer cohort only) within 14 days prior to first dose. Screening labs done within 72 hours prior to first dose can also be used for on treatment lab purposes at Day 1 dosing.
Pregnancy Test (WOCBP only)	X	Serum or urine within 24 hours of first dose
Ophthalmological evaluation (additional pancreatic cancer cohort only)	X	

Table 5.1-2: On-Study Assessments - Arm N, Nivolumab Monotherapy (CA209032)		
Procedure	For Arm N, Nivolumab is administered every 2 weeks	Notes
	Day 1 Week 1, 3, 5, 7, 9, etc	
Safety Assessments		
Targeted Physical Examination	X	Within 72 hours prior to dosing. During treatment hold to be conducted every 12 weeks to adjust to the tumor assessment schedule (see Section 3.1.6).
Vital Signs and Oxygen Saturation	X	Including BP, HR, temperature, and oxygen saturation by pulse oximetry. Pulse oximetry at rest and within 72 hours prior to dosing. During treatment hold to be conducted every 12 weeks to adjust to the tumor assessment schedule (see Section 3.1.6).
Physical Measurements (including performance status)	X	Weight and ECOG status. The dosing calculations should be based on the body weight. If the subject's weight on the day of dosing differs by > 10% from the weight used to calculate the dose, the dose must be recalculated. All doses should be rounded to the nearest milligram. During treatment hold to be conducted every 12 weeks to adjust to the tumor assessment schedule (see Section 3.1.5).
Adverse Events Assessment	Continuously	eSAEs should be approved in TAO within 5 days from entry

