Physical Measurements (including performance status)	X	Weight and ECOG status The dosing calculations should be based on the body weight. If the subject's weight on the day of dosing differs by > 10% from the weight used to calculate the dose, the dose must be recalculated. All doses should be rounded to the nearest milligram. During treatment hold to be conducted every 12 weeks to adjust to the tumor assessment schedule (see Section 3.1.6).
Echocardiogram (additional pancreatic cancer cohort only)	After the first month of treatment, then every 3 months or as clinically indicated until treatment discontinuation	In case of decrease in LVEF from baseline of greater than 10% and less than institutional LLN, follow requirements for dose modification, Section 4.5.3 . All patients restarting treatment with a dose reduction of cobimetinib should have LVEF measurements 2, 4, 10, and 16 weeks after re-start, and then as clinically indicated
Ophthalmological evaluation	X	Every 12 weeks and any time a patient reports new or worsening visual disturbances
Adverse Events Assessment	Continuously	eSAEs should be approved in TAO within 5 days from entry
		
Laboratory Tests	X	Within 72 hours prior to each dose up to and including Week 25 and then every other dose thereafter (Week 29, Week 33, Week 37 etc.). Dosing to include CBC w/ differential, LFTs, BUN or serum urea level, creatinine, albumin, Ca, Mg, Na, K, Cl, LDH, glucose, amylase, lipase, TSH (if TSH result abnormal, subsequent testing of Free T4 and Free T3 required) and CPK. During treatment hold to be conducted every 12 weeks to adjust to

Table 5.1-6: On-Study Assessments for N-I Arms (Dose Level 2d) Nivolumab + Ipilimumab + Cobimetinib Combination (CA209032)

Procedure	For Arm N-I Dose level 2d, Nivolumab is administered every 2 weeks, Ipilimumab is administered every 6 weeks, cobimetinib is administered orally 21 days on/7 days off	Notes
	Day 1 Week 1, 3, 5, 7, 9, etc	
		the tumor assessment schedule (see Section 3.1.6).
Pregnancy Test (WOCBP only)	X	Serum or urine within 24 hours prior to first dose and then every 4 weeks. During treatment hold to be conducted every 12 weeks and resume per protocol testing once treatment resumes (see Section 3.1.6).
Outcomes Research Assessments		

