Based on SCLC data so far observed in this study with an ORR of about 10% for nivolumab monotherapy and about 23% for the nivolumab + ipilimumab combination therapy, sample sizes of $N = 150$ for nivolumab monotherapy and $N = 100$ for nivolumab + ipilimumab combination therapy (nivolumab 1 mg/kg + ipilimumab 3 mg/kg) will target a Type I error rate of 5% (two-sided) and will have 78% power to detect the difference between these two arms if the true response rates are 10% and 23%, respectively.

Sample Size determination for ovarian cancer cohort

Also in Amendment 09, an ovarian cancer cohort is added and a one stage design with the treatment of 40 subjects for each combination will be used. These sample sizes will provide 79% power to reject the null hypothesis of 10% response rate, if the true response rate is 25% with a two-sided Type I error rate of 5%.

Sample Size determination for the additional pancreatic cancer cohort

A one stage design will be used, with the treatment of 30 subjects with nivolumab 3 mg/kg every 2 weeks, ipilimumab 1 mg/kg every 6 weeks, and cobimetinib 60 mg po qd 21 days on/7 days off. This sample size will provide 70% power to reject the null hypothesis of 10% response rate if the true response rate is 25% with a two-sided Type I error rate of 5%.

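### Cobimetinib triplet cohort: the cardiac entry limits are joined by *and*, so a patient with only low LVEF or only a long QTc may not be excluded

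*Protocol*

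**What the plan says.** The cardiac entry limits for the additional pancreatic cancer cohort (Arm N-I Dose Level 2d) appear in two places in Revised Protocol 07D.

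- **Table 5.1-1, Echocardiogram row.** The note excludes "Subjects with LVEF below the institutional LLN or < 50%, whichever is lower, and corrected QT" of at least 450 ms.
- **Section 3.3.2, exclusion 3d.** For this cohort it names a baseline echocardiogram with LVEF "below the institutional lower limit of normal (LLN) or < 50%, whichever is lower, and electrocardiogram with corrected QT" of at least 450 ms, and says these should be excluded.

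The ECG row of Table 5.1-1 gives only a time window, "Within 14 days prior to first dose", and no QTc threshold. Section 5.3 says only that the echocardiogram and eye examination are done in this cohort. Exclusion 2a in Section 3.3.2 is a general discretionary item covering serious or uncontrolled disorders that, "in the opinion of the investigator, may increase the risk associated with study participation or study drug administration".

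On treatment, Table 5.1-6 schedules the echocardiogram "After the first month of treatment, then every 3 months or as clinically indicated until treatment discontinuation". Section 8.1 sets the cohort size: "A one stage design will be used, with the treatment of 30 subjects with nivolumab 3 mg/kg every 2 weeks". Revised Protocol 08, in the same file, does not include this cohort and so does not bear on the question.

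**The concern.** The rule decides who may receive a three-drug regimen containing a MEK inhibitor. If low LVEF and long QTc must both be present, a patient with a clearly reduced ejection fraction and a normal QTc passes the screen, as does a patient with normal LVEF and a QTc of 450 ms or more. If either alone is enough, both are kept out. Two sites could reach opposite decisions on the same patient, and each could defend its decision from the text.

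The screening echocardiogram is the only scheduled LVEF measurement until after the first month of treatment. Section 3.3.2 ends by insisting that every eligibility criterion be fully met, so the wording itself settles entry.

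**Working it through.** No arithmetic applies. The check compares the two statements of the rule under each reading and then looks for other text that settles the matter.

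**The rule.** Let A be LVEF below the lower of the institutional LLN and 50%. Let B be corrected QT of 450 ms or more.

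| Findings at screening | Both required (A and B) | Either suffices (A or B) |
|---|---|---|
| A and B | excluded | excluded |
| A only | eligible | excluded |
| B only | eligible | excluded |
| neither | eligible | eligible |

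The readings disagree in two of the four rows, which are the two single-abnormality patterns.

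**The table note.** It has one grammatical subject, the patients, who carry both conditions. On its natural reading a patient must have A and B to be excluded.

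**Exclusion 3d.** Here the grammatical subjects are two test results, an echocardiogram and an electrocardiogram. In a list of exclusionary findings this can mean that each result is excluded, or that the two together are. The item does not say either, any or both.

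**Count of statements.** The limits are stated in 2 places, both times joined by *and*. Stand-alone statements of either limit: 0. QTc limit in the ECG row: none.

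**Neighbouring items.** Under the same heading, 3a (hepatitis B, hepatitis C) and 3b (HIV, AIDS) join findings that each exclude alone, and both use *or*. They therefore do not support reading the *and* in 3d as two separate exclusions.

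**Rules elsewhere that hint at intent.** In Table 4.5.3-1 a fall in LVEF alone leads to cobimetinib being withheld, and QTc plays no part. The echocardiogram note in Table 5.1-6 also acts on LVEF alone. After a hold for an asymptomatic fall, cobimetinib may resume only if LVEF is at or above the LLN, and is otherwise stopped for good. A patient who entered with A is already below the LLN, so after such a hold would have to exceed baseline to resume. These rules suggest that low LVEF was meant to exclude on its own. None of them states an entry criterion.

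**The case against.** The strongest reply is that Section 3.3.2 governs entry, not the procedural table, and that 3d is better read as listing two excluded results. It names two instruments and does not say the findings must coincide. Elsewhere the protocol often marks a joint condition clearly: concurrent transaminase and bilirubin elevation in Section 4.5.5, and a capitalised AND in Section 4.5.4, in the LVEF resumption rules of Table 4.5.3-1 and in the liver injury definition of Section 6.6. Table 5.1-1 also requires all criteria to be confirmed before the first dose, so a site would have to read 3d as a joint condition before enrolling a single-abnormality patient.

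Much of this is fair as evidence of intent, but it does not settle the wording. The usage is not uniform: Table 4.5.3-1 joins two LVEF conditions that must both hold with a lower-case *and*. If 3d does mean either, the table note read naturally conflicts with it. If 3d means both, a single abnormality is admitted. A correction is needed in each case.

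A second reply points to safeguards for this cohort in Section 3.1.1: daily oversight by the Medical Monitor, no more than 6 subjects enrolled per week during the first month, and a safety review once 12 patients have been followed for at least 1 month. Echocardiograms may also be done when clinically indicated. These reduce the consequences, but they are not an entry limit. Exclusion 2a acts before entry, but it rests on judgement and does not replace a threshold the protocol chose to fix.

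It is also true that the protocol does not say whether this cohort is still enrolling, so the practical benefit of rewording now is unknown.

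**Conclusion.** The concern holds. The Table 5.1-1 note, followed literally, does not exclude a patient with one cardiac abnormality; exclusion 3d can be read either way; and nothing else in the protocol resolves it. The intent was probably that either finding excludes, and that supports correcting the text.

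The scope is narrow: one single-arm cohort of 30 subjects, with no effect on power, type I error or any efficacy estimate. How many patients would be affected cannot be stated, because the protocol gives no frequency for low LVEF or long QTc. The conclusion rests on the wording alone and assumes nothing about how sites applied it. The correction should be made, because it concerns a safety entry rule and not only style.

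**What to change.** Replace exclusion 3d with two separate items for the additional pancreatic cancer cohort:

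1. baseline echocardiogram with LVEF below the institutional LLN or below 50%, whichever is lower;
2. baseline ECG with corrected QT of 450 ms or more.

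State that either alone excludes. In Table 5.1-1, keep only the LVEF limit in the echocardiogram row and move the QTc limit to the ECG row, marked as applying to this cohort only. Both thresholds stay unchanged.

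The cost is wording in two places. No procedure is added, since the echocardiogram and ECG are already required at screening. The one downside is possibly a few more screen failures.

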5.1.1 Retesting During Screening or Lead-in Period

Laboratory parameters and/or assessments that are included in [Table 5.1-1](#), Screening Procedural Outline may be repeated in an effort to find all possible well-qualified subjects. Consultation with the Medical Monitor may be needed to identify whether repeat testing of any particular parameter is clinically relevant.

5.2 Study Materials

- NCI CTCAE version 4.0
- BMS-936558 (nivolumab) Investigator Brochure
- Ipilimumab Investigator Brochure
- Laboratory manuals for collection and handling of blood (including biomarker and immunogenicity) and tissue specimens
- Site manual for operation of interactive voice response system, including enrollment worksheets
- Site manual for imaging process and requirements
- Manual for entry of local laboratory data
- Serious Adverse Events (or eSAE) case report form pages
- Pregnancy surveillance forms
- RECIST 1.1 pocket guide

5.3 Safety Assessments

At baseline, a medical history will be obtained to capture relevant underlying conditions. The baseline examinations should include signs and symptoms, weight, height, ECOG Performance Status, BP, HR, temperature, and oxygen saturation by pulse oximetry at rest should be performed within 14 days prior to first dose except where noted in 

Baseline local laboratory assessments should be done within 14 days prior to the first dose and include: CBC w/differential, LFTs (ALT, AST, total bilirubin, alkaline phosphatase), BUN or serum urea level, creatinine, albumin, Ca, Mg, Na, K, Cl, LDH, glucose, amylase, lipase, TSH, Free T4, Free T3, and Hep B and C testing (HBV sAg and HCV RNA or Ab) and CPK (additional pancreatic cancer cohort only) (see [Table 5.1-1](#)). Pregnancy testing for WOCBP (done locally) must be performed within 24 hours prior to the initial administration of study drug at baseline and then every 3 weeks for subjects in Arm N-I at Week 1-12, then every 4 weeks, and at the safety follow up visits. For subjects in Arm N and N-I 2c pregnancy testing for WOCBP (done locally) must be performed within 24 hours prior to the initial administration of study drug at baseline and then every 4 weeks, and at each safety follow up visit. During treatment hold, pregnancy testing must be performed every 12 weeks and resumed per protocol testing once treatment resumes.

Subjects will be evaluated for safety if they have received any study drug. Toxicity assessments will be performed continuously during the treatment phase. During the safety follow-up phase (Table 5.1-4) toxicity assessments should be done in person. Once subjects reach the survival follow-up phase, either in-person visits or documented telephone calls to assess the subject's status are acceptable.

Adverse events and laboratory values will be graded according to the NCI-CTCAE version 4.0.

On-study weight, ECOG performance status, and vital signs should be assessed at each on-study visit prior to nivolumab dosing. Vital signs should also be taken as per institutional standard of care prior to, during and after dosing. Oxygen saturation by pulse oximetry at rest should be assessed at each on study visit prior to nivolumab dosing. The start and stop time of the nivolumab and the ipilimumab infusion should be documented. Physical examinations are to be performed as clinically indicated. If there are any new or worsening clinically significant changes since the last exam, report changes on the appropriate non-serious or serious adverse event page.

Additional measures, including non-study required laboratory tests, should be performed as clinically indicated or to comply with local regulations. Laboratory toxicities (eg, suspected drug induced liver enzyme elevations) will be monitored during the follow-up phase via on site/local labs until all study drug related toxicities resolve, return to baseline or are deemed irreversible.

Oxygen saturation by pulse oximetry should be obtained prior to each dose of nivolumab or ipilimumab and at any time a subject has any new or worsening respiratory symptoms. A reading at rest should be obtained at each time point. If a subject shows changes on pulse oximetry or other pulmonary-related signs (eg, hypoxia, fever) or symptoms (eg, dyspnea, cough) consistent with possible pulmonary adverse events, the patient subject should be immediately evaluated to rule out pulmonary toxicity. An algorithm for the management of suspected pulmonary toxicity can be found in [Appendix 2](#).

Echocardiogram and ophthalmologic examination (including retinal evaluation) to be conducted by an ophthalmologist will be performed for the additional pancreatic cancer cohort only.

Some of the previously referred to assessments may not be captured as data in the eCRF. They are intended to be used as safety monitoring by the treating physician. Additional testing or assessments may be performed as clinically necessary or where required by institutional or local regulations.

5.3.1 Imaging Assessment for the Study

Images will be submitted to an imaging core lab for central review. Sites will be trained prior to scanning the first study subject. Image acquisition guidelines and submission process will be outlined in the CA209032 Imaging Manual to be provided by the core lab. Any incidental findings of potential clinical relevance that are not directly associated with the objectives of the protocol should be evaluated and handled by the Study Investigator as per standard medical/clinical judgment.

CT/MRI

Contrast-enhanced Computed Tomography (CT) scans acquired on dedicated CT equipment is preferred for this study. CT with contrast of the chest, abdomen and pelvis are to be performed for tumor assessments at baseline and beginning 6 weeks (+/- 1 week) from first dose and continuing every 6 weeks (+/- 1 week) for the first 24 weeks and every 12 weeks (+/- 1 week) thereafter, while on treatment or on treatment hold for any reason until disease progression and treatment discontinuation, whichever occurs later. Additionally, with the exception of crossover participants, tumor assessments will not be required upon initiation of subsequent anti-cancer therapy. CT scans should be acquired with 5mm slices with no intervening gap (contiguous). Although a contrast enhanced CT in particular for the chest is the preferred technique, a contrast enhanced MRI may be used based on local standards.

Should a subject have a contraindication for CT IV contrast, a non-contrast CT of the chest and a contrast enhanced MRI of the abdomen and pelvis may be obtained. MRI's should be acquired with slice thickness of 5 mm with no gap (contiguous).

Every attempt should be made to image each subject using an identical acquisition protocol on the same scanner for all imaging time points.

Note: Use of CT component of a PET/CT scanner:

Combined modality scanning such as with FDG-PET/CT is increasingly used in clinical care, and is a modality/technology that is in rapid evolution; therefore, the recommendations outlined here may change rather quickly with time. At present, low dose or attenuation correction CT portions of a combined FDG-PET/CT are of limited use in anatomically based efficacy assessments and it is therefore suggested that they should not be substituted for dedicated diagnostic contrast enhanced CT scans for anatomically based RECIST measurements. However, if a site can document that the CT performed as part of a FDG-PET/CT is of identical diagnostic quality to a diagnostic CT (with IV and oral contrast) then the CT portion of the FDG-PET/CT can be used for RECIST 1.1 measurements. Note, however, that the FDG-PET portion of the CT introduces additional data which may bias an investigator if it is not routinely or serially performed.

MRI Brain

MRI or CT of brain is required at screening in order to rule out active metastatic disease. For patients with a history of known brain metastasis, an MRI brain is required at baseline. A CT brain is not allowed for patients with known brain metastasis at baseline. Subjects with a history of brain metastasis should have surveillance MRI approximately every 12 weeks, or sooner if clinically indicated.

